15.2.3. Safety Population

The Safety Population comprises all subjects in the ITT Population who receive at least one dose of study treatment and will be based on the actual treatment received.

15.2.4. Pharmacokinetic Population

The PK Population comprises all subjects who receive at least one dose of IMO-2125 with at least one measurable concentration of IMO-2125.

15.3. Missing Data

Missing data occurs when any requested data is not provided, leading to blank fields on the collection instrument. These data will be indicated by the use of a “blank” in subject listing displays. Answers such as “Not applicable” and “Not evaluable” are not missing.

All available OS, PFS, and duration of response data will be analyzed using suitable statistical methods; subjects with shorter treatment and follow-up due to the natural history of their disease, or medical necessities of the treatment of their disease will not be considered to have missing time-to-event data. For ORR and DRR, all subjects in the ITT population will be included in the denominator when calculating the percentages; that is, the imputed response will be negative. Missing QoL data from the EORTC QLQ-C30 will be imputed using the methods prescribed for EORTC QLQ instruments.

Subjects with the designation of treatment relationship for AEs and SAEs missing will have the worst case assumed to impute the relationship: if relationship to study treatment is missing it will be assumed to be “Yes”.

Partial dates will be imputed for AEs and concomitant medications. Imputed dates are will not be used for deriving the last contact date for OS. Imputed dates will be displayed in listings and identified as imputed. Full details of imputing missing data and rules for analysis of measures with missing data will be included in the Statistical Analysis Plan (SAP).

15.4. Analysis of Efficacy

In this study, ORR and OS comprise a primary endpoint family; both have a priori hypotheses and will be tested for statistical significance. ORR will be tested first followed by OS. The fallback method for the primary endpoint family will be applied to control the study-wise Type I error rate.

Under the fallback method, $\alpha_1 = 0.02$ is assigned to the one-sided ORR test and an alpha of 0.005 is saved for the one-sided OS test.

- If the ORR test is significant at $\alpha_1 = 0.02$, this alpha is unused and will be passed to the OS test as an additional alpha of 0.02, giving a total alpha for the OS test of 0.025. The OS test will then be performed at the significance level of 0.025.
- If the ORR test is not significant at 0.02 level, then this alpha of 0.02 will not be available to be passed on for the OS test. The OS test will be performed at the originally reserved alpha of 0.005.

Full details of all efficacy analyses will be in the SAP. All efficacy analyses will use the ITT Population.

15.4.1. Analysis of the Family of Primary Endpoints

15.4.1.1. Analysis of Objective Response Rate

The analysis of ORR (assessed by blinded independent review using RECIST v1.1) will be performed using a CMH test comparing the ORR for the two treatment groups controlling for the randomization strata. This is the only test of RECIST v1.1 ORR that will be done. The analysis of ORR will take place when all randomized subjects fall within one of the following categories:

- completed scheduled study treatment and completed at least 28 weeks on the study;
- prematurely discontinued study treatment and completed at least 28 weeks on the study;
- withdrew, were lost to follow-up, or died before completing at least 28 weeks on the study.

15.4.1.2. Primary Analysis of Overall Survival

Overall survival, defined as the time in months from randomization to death from any cause, will be analyzed using the Kaplan-Meier method after approximately 392 deaths have occurred, or approximately 36 months after the last subject is randomized, whichever occurs first. Sensitivity analyses will be detailed in the SAP.

The study hypotheses will be tested using a one-sided, stratified log-rank test. If the null hypothesis is rejected at the appropriate alpha level in accordance with the fallback method, it will be concluded that OS in the IMO-2125 + ipilimumab combination arm is statistically significantly superior to the OS in the ipilimumab alone arm.

Stratification factors will include duration of prior anti-programmed death receptor-1 (PD-1) therapy (≥ 12 weeks vs < 12 weeks), metastasis stage (M1c vs other), and BRAF mutation status and prior targeted therapy (BRAF wild type, BRAF mutation positive with prior targeted therapy, or BRAF mutation positive with no prior targeted therapy) using block randomization. Targeted therapy is the use of an approved BRAF or MEK inhibitor alone or in combination. Stratification will use block randomization. Depending on the distribution of the strata with the ITT, strata may be collapsed as appropriate. The full details will be specified within the SAP.

Subjects who have not died or who are lost to follow up at the data cut-off date will be censored at the last date they were known to be alive.

Amounts and patterns of missing PRO data from the EORTC QLQ-C30 instrument in the two arms will be described using counts and percentages and with appropriate figures. Scores and changes from baseline in scores will be reported by visit. A mixed model for repeated measures data will be used with treatment arm and stratification factors (as used in the primary analysis of OS) included as independent variables. There will be no statistical tests of EORTC QLQ-C30 data; all analyses will be descriptive.

15.5. Analysis of Safety

All safety analyses will use the Safety Population.

All safety measures, including vital signs, laboratory values, ECOG performance status, and ECG values will be summarized descriptively; no formal statistical hypotheses will be tested.

For laboratory values that are continuous, shift tables from baseline by scheduled visit and to worst case on study will be produced. Worst case will be relative to the normal range for laboratory values that are not in the CTCAE; otherwise, the worst case will be the highest CTCAE grade. For laboratory values that are bi-directional, separate shift summaries will be produced; for example, for shifts in CTCAE grade, both hypokalemia and hyperkalemia shifts will be shown. Only scheduled visits will be included in the shift tables by visit; all visits will be included when determining the worst case on study.

Adverse events will be tabulated by Medical Dictionary for Regulatory Activities (MedDRA) System Organ Class and Preferred Term for each treatment arm. Adverse event summaries will include: overall, by severity, related AEs, SAEs, irAEs, and AEs leading to discontinuation of study treatment.

Concomitant medications will be coded by World Health Organization drug class and Anatomical Therapeutic Chemical text and summarized by treatment arm.

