## **5 CHANGES IN THE CONDUCT OF PLANNED ANALYSES**

There are no planned analyses that differ from those specified in the protocol.

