## **7 GENERAL CONSIDERATIONS**

Analysis datasets will be created according to Clinical Data Interchange Standards Consortium (CDISC) standards, and data will be displayed according to reporting standards in this SAP and TLF formats.

SAS Version 9.4 or higher will be used to perform all data analyses and to generate tables, listings, and figures (TLFs).

All data collected in the database will be presented in data listings.

Idera Pharmaceuticals, Inc.  
Statistical Analysis Plan  
Protocol Number: 2125-MEL-301

---

For each subject, data up to the time of study completion, lost to follow-up, or withdrawal from study will be included in the appropriate analysis sets defined in [Section 6](#).

Continuous variables will be summarized in terms of the number of observations, mean, standard deviation, median, minimum, and maximum. Other descriptive statistics (e.g., quartiles, coefficient of variation) may be reported when appropriate. Categorical variables will be summarized using frequency counts and percentages. Analyses that use other descriptive statistics will be specified in the applicable SAP section.

Summaries will order displays by ipilimumab with IMO-2125 first, followed by the ipilimumab alone arm. Unless otherwise stated, summaries and figures will be reported by study arm. Summary statistics of central tendency will use one more decimal place than the collected data. Summary statistics of variability will use one more decimal place than the corresponding measure of central tendency. For example, the mean and median for age in years will be presented to one decimal place and the standard deviation of age will be reported to 2 decimal places. Percentages will be displayed to one decimal place, and proportions will be displayed to 4 decimal places. Durations for treatment exposure (weeks), adverse events (weeks), and response (months) will be displayed to 1 decimal place.

Planned visits will be used in all tables and figures that are by visit. Generally, only planned visits will be used in the summaries, statistical analyses, and calculations of any derived parameters; unscheduled visits will be included in the listings. However, both unscheduled and scheduled visits will be included in the determination of the worst-case (highest and/or lowest) post-baseline shifts for laboratory results, vital signs, and ECG.

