## **9.3 DEMOGRAPHIC AND BASELINE DISEASE CHARACTERISTICS**

The following summaries will be provided:

Idera Pharmaceuticals, Inc.  
Statistical Analysis Plan  
Protocol Number: 2125-MEL-301

---

- Demographic and baseline characteristics (age at consent, age categories [18-65, >65-75, >75], race, ethnicity, sex, country, region, height, weight, BMI, baseline lactate dehydrogenase [LDH], LDH categories [ $\leq$ ULN, >ULN], baseline neutrophil/lymphocyte ratio, and ratio categories [ $<2.5$ ,  $\geq 2.5$ ])
- Baseline disease characteristics (primary histology, stage, tumor PD-L1 immunohistochemistry result, elevated LDH, BRAF mutation status, and ECOG performance status at baseline)
- Prior systemic anticancer treatment history (all settings)
- Prior systemic anticancer treatment history (unresectable/metastatic disease setting only)

The following listings will be provided:

- Demographic characteristics
- Baseline disease characteristics (excluding ECOG performance status)
- Medical history
- Prior systemic anticancer treatment, including best response and reason for discontinuation if available
- Prior cancer-related surgeries
- Prior radiotherapy
- ECOG performance status

The demographic and baseline disease characteristics analyses will be repeated for FAS and Per Protocol Analysis Set for sensitivity analysis.

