## **11.9 OTHER SAFETY MEASURES**

The denominator in percentage calculations at each scheduled visit will be based on the number of subjects with non-missing values at each visit.

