## 16.2 LIST OF TABLES, LISTINGS, AND FIGURES

The IDMC TLFs will be generated based on the schedule as defined in the Charter. The analysis of ORR will take place after all the randomized subjects either completed scheduled study treatment and completed at least 28 weeks on the study, prematurely discontinued study treatment and completed at least 28 weeks on the study, or withdrew, were lost to follow-up, or died before completing at least 28 weeks on the study. The final study analysis will take place when 392 deaths or approximately 36 months after the last subjects is randomized, whichever occurs first. All tables, figures, and listings will be produced for the final study analysis.

Tables, figures, and listings that will be produced for the IDMC meetings are identified with IDMC, the additional TLFs requested by IDMC during the course of the study are confidential and will not be included in the list below; and the final analysis of objective response rate with ORR, and the final analysis of OS with Final. The page header will indicate the timing of the analysis.

Table Title	Timing of Analysis
14.1.1.1 Subject Disposition, All Subjects *	IDMC, ORR, Final
14.1.1.2 Subject Disposition, Full Analysis Set	ORR, Final
14.1.1.3 Subject Disposition, Per Protocol Analysis Set	ORR, Final
14.1.2 Duration of Active Follow-up Times, Intent to Treat Analysis Set	ORR, Final
14.1.3 Major Protocol Deviations by Category, Intent to Treat Analysis Set	ORR, Final
14.1.4.1 Demographic Characteristics, Intent to Treat Analysis Set *	IDMC, ORR, Final
14.1.4.2 Demographic Characteristics, Full Analysis Set	ORR, Final
14.1.4.3 Demographic Characteristics, Per Protocol Analysis Set	ORR, Final
14.1.5.1 Baseline Disease Characteristics, Intent to Treat Analysis Set	IDMC, ORR, Final
14.1.5.2 Baseline Disease Characteristics, Full Analysis Set	ORR, Final
14.1.5.3 Baseline Disease Characteristics, Per Protocol Analysis Set	ORR, Final
14.1.6.1 Prior Systemic Anticancer Treatment History in All Settings, Intent to Treat Analysis Set	IDMC, ORR, Final

Idera Pharmaceuticals, Inc.  
 Statistical Analysis Plan  
 Protocol Number: 2125-MEL-301

Table Title	Timing of Analysis
14.1.6.2 Prior Systemic Anticancer Treatment History in Unresectable/Metastatic Disease Setting Only, Intent to Treat Analysis Set	ORR, Final
14.1.7.1 Stratification Factor Levels as Randomized, Intent to Treat Analysis Set	ORR, Final

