14.1.7.2 Stratification Factor Levels from the Clinical Data, Intent to Treat Analysis Set	ORR, Final
14.1.8.1 Concomitant Medications, Safety Set	ORR, Final
14.1.8.2 Concomitant Medications for irAEs by Category, Safety Set	IDMC, ORR, Final
14.1.8.3 Cancer Treatments and Surgeries after Start of Study Treatment, Safety Set	ORR, Final
14.2.1.1.1 Summary of Independent Reviewer-Assessed Response by RECIST v1.1, Intent to Treat Analysis Set *	ORR, Final
14.2.1.1.2 Sensitivity Analysis: Summary of Objective Response Rate by RECIST v1.1, Full Analysis Set	ORR, Final
14.2.1.1.3 Sensitivity Analysis: Summary of Objective Response Rate by RECIST v1.1, Per Protocol Analysis Set	ORR, Final
14.2.1.1.4 Sensitivity Analysis: Un-Stratified and Best Case Scenario Analysis of Objective Response Rate by RECIST v1.1, Full Analysis Set	ORR, Final
14.2.1.2 Summary of Investigator-Assessed Response by RECIST v1.1, Intent to Treat Analysis Set *	ORR, Final
14.2.1.3.1 Concordance of Best Overall Response by Independent Reviewer and Investigator, Intent to Treat Analysis Set *	ORR, Final
14.2.1.3.2 Concordance of Objective Response Rate by Independent Reviewer and Investigator, Intent to Treat Analysis Set	ORR, Final
14.2.1.4.1 Subgroup Analysis: Summary of Objective Response Rate by RECIST v1.1 by Metastasis Stage, Intent to Treat Analysis Set	ORR, Final
14.2.1.4.2 Subgroup Analysis: Summary of Objective Response Rate by RECIST v1.1 by BRAF Mutation and Prior Targeted Therapy, Intent to Treat Analysis Set	ORR, Final

Idera Pharmaceuticals, Inc.  
 Statistical Analysis Plan  
 Protocol Number: 2125-MEL-301

Table Title	Timing of Analysis
14.2.1.4.3 Subgroup Analysis: Summary of Objective Response Rate by RECIST v1.1 by Duration of Prior Anti-PD-1 Therapy, Intent to Treat Analysis Set	ORR, Final
14.2.1.4.4 Subgroup Analysis: Summary of Objective Response Rate by Country, Intent to Treat Analysis Set	ORR, Final
14.2.1.4.5 Subgroup Analysis: Summary of Objective Response Rate by Baseline ECOG, Intent to Treat Analysis Set	ORR, Final
14.2.1.4.6 Subgroup Analysis: Summary of Objective Response Rate by Baseline LDH, Intent to Treat Analysis Set	ORR, Final
14.2.1.4.7 Subgroup Analysis: Summary of Objective Response Rate by RECIST v1.1 by Baseline Neutrophil/Lymphocyte Ratio, Intent to Treat Analysis Set	ORR, Final

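### The protocol promises a descriptive Safety Population summary of ECOG performance status; the SAP plans none and declares no difference from the protocol

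*Protocol*

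**What the plan says.** **Protocol.** Section 6.2 names ECOG within the secondary safety endpoint, and 12.3.3 places it among the other safety assessments. Section 15.5 assigns all safety analyses to the Safety Population and states: "All safety measures, including vital signs, laboratory values, ECOG performance status, and ECG values will be summarized descriptively". Tables 1 and 2 schedule ECOG repeatedly during treatment in both arms.

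**SAP.** Section 4.1 repeats ECOG as part of the secondary safety endpoint. Section 11.9, on other safety measures, opens with a general rule ("The denominator in percentage calculations at each scheduled visit will be based on the number of subjects with non-missing values at each visit") and then has only two subsections: 11.9.1 on vital signs and weight, and 11.9.2 on ECG. The rule in section 7 that brings in unscheduled visits applies to "the determination of the worst-case (highest and/or lowest) post-baseline shifts for laboratory results, vital signs, and ECG"; ECOG is not named. Section 9.3 puts ECOG among the baseline disease characteristics ("elevated LDH, BRAF mutation status, and ECOG performance status at baseline") and also plans an ECOG listing. Section 10.1.6 uses baseline ECOG as a subgroup factor. Section 5 states: "There are no planned analyses that differ from those specified in the protocol".

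**The concern.** The protocol names four safety measures in one sentence and commits to summarising each. The SAP implements three. If the SAP is followed exactly, the study report will contain no by-arm summary of performance status during treatment, although sites rate it at several visits and it is a named endpoint component.

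The declaration in SAP 5 makes this harder to notice, because a reader relying on it would not look for a gap. The SAP's own safeguard would not catch it either: section 7 promises that the study report will identify departures from the SAP, and here the SAP itself departs from the protocol.

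**Working it through.** The plan states no figure to reproduce. The check sets the protocol's commitment beside the SAP's planned outputs and then counts.

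**Step 1: the four measures named in Protocol 15.5.**

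| Measure | SAP text | Safety Set tables in SAP 16.2 |
|---|---|---|
| Laboratory values | 11.8 | 14.3.8.1 to 14.3.8.7 |
| Vital signs | 11.9.1 | 14.3.9.1, 14.3.9.2 |
| ECG | 11.9.2 | 14.3.9.3 to 14.3.9.5 |
| ECOG | none in section 11 | none |

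**Step 2: every SAP output that uses ECOG.**

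- Baseline characteristics: Tables 14.1.5.1, 14.1.5.2 and 14.1.5.3, for the ITT, Full Analysis and Per Protocol sets. The first is titled "14.1.5.1 Baseline Disease Characteristics, Intent to Treat Analysis Set"; SAP 9.3 supplies the ECOG content. That is 3 tables.
- Efficacy subgroups by baseline ECOG: Table 14.2.1.4.5 ("14.2.1.4.5 Subgroup Analysis: Summary of Objective Response Rate by Baseline ECOG, Intent to Treat Analysis Set") and its OS counterpart, 14.2.3.4.5. That is 2 tables.
- Subgroup forest plots for ORR and OS: Figures 14.1.1 and 14.1.6, whose factors come from SAP 10.1.6. That is 2 figures.
- Listing 16.2.1.2.7, ITT. That is 1 listing.

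Tables: 3 + 2 = 5, all using the baseline value. Tables and figures together: 5 + 2 = 7, all at baseline. In the Safety Set: 0. Aggregate post-baseline ECOG outputs: 0.

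**Step 3: scheduled assessments left without a summary (Protocol Tables 1 and 2).**

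- Arm A: Weeks 4, 7, 10 and 14, so 4 visits.
- Arm B: Weeks 5, 8, 11, 16, 20 and 24, so 6 visits.

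These counts take the Week 1 rating as pre-dose, which the schedule does not state for ECOG. If it were taken after dosing, the counts would be 4 + 1 = 5 and 6 + 1 = 7.

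**Step 4: was the removal recorded?** The SAP modification history records other removals, such as the irRECIST summaries and the QoL missing-assessment analysis. It mentions none for ECOG.

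**Step 5: which visits can be compared?** The second, third and fourth ipilimumab doses fall at Weeks 4, 7 and 10 in Arm A and at Weeks 5, 8 and 11 in Arm B. ECOG is rated at all of them, giving three matched pairs, one week apart. After these, Arm A has one more rating (Week 14) and Arm B three (Weeks 16, 20 and 24). Arm B thus has 6 − 4 = 2 more ratings in all, and its last is 24 − 14 = 10 weeks later.

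**The case against.** **The protocol promises little.** Section 15.5 asks only for a descriptive summary. It specifies shift and worst-case tables for laboratory values and nothing similar for ECOG. A reader might infer that the protocol promised a post-baseline or shift table of ECOG; its wording does not go that far. What it does promise is a summary of ECOG as a safety measure in the Safety Population. A baseline row in three efficacy sets is not that.

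**The values are listed.** SAP 7 says "All data collected in the database will be presented in data listings" and sorts listings by treatment arm. Listing 16.2.1.2.7 is planned at both the ORR and final analyses. A reader might therefore infer too much in saying that the SAP gives no on-treatment ECOG information by arm. That is not supported: the individual values should appear, grouped by arm. The gap is the aggregate summary, since a subject listing in the ITT set does not provide one.

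**Section 16.2 is not a complete index.** The combined-strata summary promised in SAP 9.4 and the CYP-substrate summary promised in 9.5 also have no table title there, and mock displays sit in separate documents. So absence from 16.2 alone would prove little. The point rests mainly on section 11, whose text plans no ECOG summary.

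**SAP 5 could be read narrowly.** An omitted output might be called incompleteness and not a planned analysis that differs. This is arguable, but the protocol plans this summary and the SAP does not, so the declaration is inaccurate as a guide to the differences.

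**Related data exist.** QLQ-C30 functioning (SAP 13.3) and graded adverse events cover nearby ground. This lowers the stakes, but neither is the clinician-rated measure that the protocol names.

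**Conclusion.** The point holds as a minor mismatch between the protocol and the SAP. A summary that the protocol specifies, for a named component of the secondary safety endpoint, is absent from the SAP, and SAP 5 does not disclose it. The size is zero Safety Set outputs for ECOG, with 4 scheduled post-baseline ratings in Arm A and 6 in Arm B left without an aggregate summary.

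This rests on two assumptions: that Week 1 ECOG is pre-dose, which affects only the visit counts, and that Listing 16.2.1.2.7 holds the post-baseline values, as SAP 7 implies.

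The effect is confined to descriptive safety reporting. A reader might infer that data are lost, that the summary was dropped on purpose, or that efficacy conclusions are at risk. The documents support none of these: the ratings are collected and listed, nothing records a decision to drop the summary, and ECOG enters the efficacy outputs only as a baseline characteristic or subgroup factor.

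**What to change.** Add an ECOG subsection to SAP 11.9 and one Safety Set table, by arm, to SAP 16.2.

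- **Main display:** shift from baseline at the matched visits (Weeks 4/5, 7/8 and 10/11), with the number assessed at each. SAP 13.3 already treats Weeks 7 and 8 as one visit for QLQ-C30, so the pairing has a precedent.
- **Worst post-baseline shift, if wanted:** restrict it to a common window, for example through Week 10/11. Otherwise keep it clearly secondary, with a footnote giving the unequal schedules (Arm A, 4 visits to Week 14; Arm B, 6 visits to Week 24). An unrestricted worst-case comparison gives Arm B more and later chances to record deterioration, so it is tilted against the combination. If this display is used, add ECOG to the worst-case sentence in SAP 7. The QTcF shift table (14.3.9.4) offers a ready format.
- **Alternative:** if the sponsor prefers a listing only, declare in SAP 5 that on-treatment ECOG will be listed and not summarised.

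The cost is one descriptive table and a few lines of SAP text, or a sentence in SAP 5. No new data are needed.
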